3.7. Sample size and justification

We estimate that 20% of patients who have had primary total knee replacement will have long-term post-surgical pain. Based on our recent trial in total knee replacement (Wylde V, 2015), we estimate conservatively that we will achieve a recruitment rate of 40% (an 8% conversion rate for number randomised out of those screened). Surgical audit data show that the four trial centres conduct over 1,900 primary total knee replacement procedures annually. Over 30 months, this equates to 4,750 procedures, and we estimate that 950 of these patients will have long-term post-surgical pain. With a recruitment rate of 40% we can recruit 380 patients over this period. In our recent trial we achieved 83% follow-up (Wylde et al, 2015); therefore, allowing for a generous 25% loss to follow-up in the STAR trial, a total of 380 participants randomised would yield 285 for analysis. For a 2:1 intervention:control randomisation ratio we would have a power of 80% to 90% to detect standardised differences of between 0.35 to 0.40 standard deviations (SDs) using a 2-sided 5% significance level. From previous studies (Dworkin RH, 2008), (Bruce J, 2014), the SDs for each of the BPI Interference and Pain Severity scales for patients with long-term postsurgical pain has been observed to be approximately 2, in which case the target effect size translates to a difference between intervention and control groups of between 0.7 and 0.8 scale points for both scales. Such a difference would be worthwhile detecting clinically, since the current consensus statement indicates that differences of approximately one scale point can be deemed the minimally important difference for both of these scales (Bruce J, 2014),(Kroenke K, 2009).

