7.6.4 Repeated measures analysis

A repeated measures analysis will be performed using a multi-level mixed effects linear regression to model each of the BPI subscales (measured at 6 months and 12 months) on the baseline measure of the outcome, stratification variables and any variables which show imbalance at baseline. The repeated measures model will also include an interaction between the intervention allocation and the time point. The p-value of the interaction term will be the focus of analysis. This analysis will account for clustering within patient using a random effect. The analysis will include those patients who have at least one non-missing outcome over the two time-points. The results of this analysis will be presented in **Table 45**.

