Comparison of results of ITT analysis of complete cases with per protocol analysis and CACE for Secondary outcome of **Self-Administered Patient Satisfaction Scale for Primary Hip and Knee Arthroplasty**. *Table 39: Sensitivity analysis secondary endpoint results*

	Ν	Difference in means ^a	95% CI	p-value
ITT				
Per protocol				
CACE analysis				

^a Adjusted for trial centre and for baseline OKS

Comparison of results of ITT analysis of complete cases with per protocol analysis and CACE for Secondary outcome of **ICECAP-A**.

Table 40: Sensitivity analysis secondary endpoint results

	Ν	Difference in means ^a	95% CI	p-value	
ITT					
Per protocol					
CACE analysis					

^a Adjusted for trial centre and for baseline OKS

Comparison of results of ITT analysis of complete cases with per protocol analysis and CACE for Secondary outcome of **Short form-12**.

Table 41: Sensitivity analysis secondary endpoint results

	Ν	Difference in means ^a	95% CI	p-value
ITT				
Per protocol				
CACE analysis				

^a Adjusted for trial centre and for baseline OKS

Comparison of results of ITT analysis of complete cases with per protocol analysis and CACE for Secondary outcome of **Hospital Anxiety Scale (HADS: Anxiety)**.

Table 42: Sensitivity analysis secondary endpoint results

	Ν	Difference in means ^a	95% CI	p-value
ITT				
Per protocol				
CACE analysis				

^a Adjusted for trial centre and for baseline OKS

Comparison of results of ITT analysis of complete cases with per protocol analysis and CACE for Secondary outcome of **Hospital Depression Scale (HADS: Depression)**.

Table 43: Sensitivity analysis secondary endpoint results

	Ν	Difference in means ^a	95% CI	p-value
ITT				
Per protocol				
CACE analysis				

^a Adjusted for trial centre and for baseline OKS

Comparison of results of ITT analysis of complete cases with per protocol analysis and CACE for Secondary outcome of **Chronic Widespread Pain (Body Map)**.

Table 44: Sensitivity analysis secondary endpoint results

	Ν	Odds Ratio ^a	95% CI	p-value
ITT				
Per protocol				
CACE analysis				

^a Adjusted for trial centre and for baseline OKS

Repeated measures analysis

Table 45: Repeated measures analysis of BPI subscales

	Intervention		Usual Care				
	N groups	Average obs per group	N groups	Average obs per group	Difference in means	95% CI	P-value
BPI Pain subscale							
BPI Interference subscale							

*adjusted for:

Table 46: Compliance

	Number of patients	Number of patients who	Compliance (%)

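### The repeated-measures sensitivity analysis focuses on a p-value that tests only whether the effect changes between 6 and 12 months, so it cannot support or contradict the primary result

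*SAP*

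**What the plan says.** Section 7.6.4 is one of the sensitivity analyses under SAP section 7.6. It models each BPI subscale with a multilevel linear model. The outcome rows are the 6- and 12-month scores. The baseline score enters as a covariate, alongside the stratification variables and any variables imbalanced at baseline. A patient random effect handles the repeated scores, and patients with at least one of the two follow-up scores are included. The model contains an allocation-by-time interaction, and the section then states: "The p-value of the interaction term will be the focus of analysis". It does not name the effect at 6 months, at 12 months or averaged over both as a quantity to be reported.

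The results shell, "Table 45: Repeated measures analysis of BPI subscales", has one row per subscale, with a single difference in means, one 95% CI and one p-value. It has no row for either visit and none for the interaction.

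**The concern.** What the interaction means depends on which visits are outcomes. If baseline were an outcome row, an allocation-by-time term could carry the treatment effect. Here baseline is a covariate, so the term measures only how the effect moves from 6 to 12 months.

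A sensitivity analysis is normally read beside the primary result to see whether that result holds under a different approach. This one does not speak to that question as specified. A sustained benefit would give a null interaction. A significant interaction could mean a benefit that emerges late or one that is lost, and its p-value does not distinguish the two.

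Table 45 adds to the difficulty. With the interaction in the model and the usual indicator coding, the allocation coefficient is the effect at the reference visit only. One analyst might enter that coefficient, another the 12-month contrast, and a third might place the interaction p-value beside a treatment difference. Section 1 of the SAP says that the plan should let others carry out the analysis, and this shell does not settle what they would report.

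**Working it through.** **Inputs.** From SAP section 3.7: 285 analysed at 2:1, so 190 intervention and 95 control; an SD that "has been observed to be approximately 2"; a target difference "between 0.7 and 0.8 scale points for both scales", which is 0.35 to 0.40 SD; testing "using a 2-sided 5% significance level". No separate level is given for 7.6.4, so 5% two-sided is assumed there. The correlation r between a patient's 6- and 12-month scores is not given; r = 0.5 to 0.8 is assumed.

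**The SAP's own figure.** The standard error of a difference at one visit, in SD units, is s = √(1/95 + 1/190) = 0.1257, or 0.251 scale points at SD 2. By the normal approximation:
- 0.35 SD: 0.35/0.1257 = 2.785, power 79.5%.
- 0.40 SD: 0.40/0.1257 = 3.183, power 88.9%.

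This agrees with the stated 80% to 90%.

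**What the interaction estimates.** Let D6 and D12 be the treatment differences at the two visits. The interaction is D12 − D6. With a common SD and complete pairs:
- SE(D12 − D6) = s√(2(1 − r)): 0.1257 at r = 0.5 and 0.0795 at r = 0.8.
- SE((D6 + D12)/2) = s√((1 + r)/2): 0.1088 at r = 0.5 and 0.1192 at r = 0.8.

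**Results for a 0.8-point (0.40 SD) effect at 12 months.**

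| Effect at 6 / 12 months (points) | Quantity tested | Probability of p < 0.05 |
|---|---|---|
| 0.8 / 0.8 | Interaction | 5.0% for any r |
| 0.8 / 0.8 | Either visit alone | 88.9% |
| 0.8 / 0.8 | Average of both visits | 95.7% (r = 0.5) to 91.9% (r = 0.8) |
| 0.4 / 0.8 | Interaction | 35.7% (r = 0.5) to 71.1% (r = 0.8) |
| 0 / 0.8 | Interaction | 88.9% (r = 0.5) to 99.9% (r = 0.8) |

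In the first row D12 − D6 = 0, so the rejection rate equals alpha whatever the benefit. Simulation (10,000 trials per setting; constant benefits of 0.35, 0.40 and 1.0 SD; r = 0.5 and 0.7) gave 4.8% to 5.2%. The last row applies equally to 0.8 points at 6 months and none at 12, because the two-sided test is symmetric.

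**The case against.** The best defence is that the interaction is a valid test of a narrower question, whether the effect changes between visits, and that the SAP never says it tests efficacy. That stands, and it limits four stronger readings that a reader might infer.

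- **That the test is underpowered, at 5%.** The 5% is the type I error rate. A constant benefit is the null hypothesis, and any correctly sized interaction test behaves this way. The figure shows that the question differs from the primary one; it does not show a faulty test.
- **That the trial's efficacy conclusion is at risk.** Efficacy rests on the linear regressions in 7.3, which do not depend on 7.6.4.
- **That the main safeguard against missing data is misdirected.** Sections 4.3 and 7.6 give that role to multiple imputation and to best- and worst-case scenarios, with Tables 17 and 18 for the co-primary scales. The imputation model includes the outcome at other follow-up times, so it already uses information from patients seen only once.
- **That Table 45 rules out showing both visits.** Section 1 calls the shells a guide whose layout may change, and section 7.2 already plots both arms at each visit with confidence intervals.

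The defence does not explain how an analysis filed under sensitivity analyses, with this focus, bears on the primary result. Nor does it say which difference belongs in Table 45. Section 1 lets the layout change, but the content must stay consistent, and the content is what is undefined.

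**Conclusion.** The point holds as a defect in one supportive analysis and should be fixed; it changes no primary inference. The stated focus tests only change in effect between 6 and 12 months, and the results table does not identify the quantity it reports.

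The reading of the interaction follows from the model as described. The 5% figure does not depend on the correlation; it ignores floor effects on the 0 to 10 scale. The 89% figure uses only the SAP's planning inputs. The 92% to 96% and 36% to 71% ranges rest on the assumed correlation of 0.5 to 0.8, and the second also on an illustrative 0.4-then-0.8 pattern that is not in the SAP. All figures take 285 patients seen at both visits and count no gain from baseline adjustment.

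**What to change.** In section 7.6.4, name as the main outputs the adjusted treatment differences at 12 months and at 6 months, and their average, each with a 95% CI and obtained as contrasts from the mixed model already specified. Keep the interaction p-value, described as a test of whether the effect changes between the two visits, and say that it is not evidence for or against benefit.

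In Table 45, give each subscale a row for 6 months, a row for 12 months, a row for the average and a labelled interaction row.

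The cost is a few sentences, a revised shell, an entry in Table 51 and one post-estimation step. The fitted model, the data collected and the primary analysis stay as they are.

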7.7. Exploratory/other analysis

We recognise that there will be low power for subgroup and exploratory analyses and therefore only cautious conclusions will be drawn from them.

7.7.1 Exploratory analysis

Exploratory analyses such as CACE methodology will be used to estimate the effect in those patients able to comply with their allocated intervention.

7.7.2 Subgroup analysis

Subgroup analyses on the primary outcomes will be performed by introducing appropriate interaction terms between the intervention group and other patient characteristics in the regression models, to investigate any differential effects in certain subgroups of the population. These factors will be trial centre and baseline Oxford Knee Score. The OKS will be treated as a continuous variable ranging 0-48; however, for descriptive purposes we will consider the conventional categories of: 0-19 (severe knee arthritis); 20-19 (moderate to severe knee arthritis); 30-39 (moderate knee arthritis) and 40-48 (satisfactory joint function).

Another subgroup analysis will be performed for those sites who limit patients who are less than 1 hour drive away versus those who accept all patients regardless of the distance from site.

The Pain Solution (PaSol) Questionnaire measures two opposing modes of coping with pain. First, 'assimilative coping' captures the style in which patients increase effort and tenaciously pursue their goal of pain control. Patients scoring high on the 'solving pain' subscale and low on the 'meaningful life despite pain' and 'acceptance of the insolubility of pain' sub-scales are high in assimilative pain coping. Second, 'accommodative coping' captures the style in which patients accept that there is unlikely to be a cure for pain and a switch in goals to living with pain is a sensible next step. Patients scoring low on the 'solving pain' subscale and high on the 'meaningful life despite pain' and 'acceptance of the insolubility of pain' sub-scales are high in assimilative pain coping. There is a strong possibility that those with different coping profiles will respond differently to intervention. Subgroup analyses will be performed using baseline PASOL data to investigate differential effects on outcomes through the use of the relevant interaction terms in regression models. First a (continuous) composite score on a single dimension of accommodative to assimilative scale will be created using an established algorithm (Geert Crombez, 2008) based on simple summation of scores accounting for their logical direction(s). Second, a three-category scale will be produced as follows: a) high in assimilative and low in accommodative; b) no clear preference; c) low in assimilative and high in accommodative. The exact determination of the thresholds inherent in the categorical version will be influenced both by the category labels of the underlying items/scores and their frequencies – for example, both taking into consideration any clear modality in the frequency distribution and so that none of the above three categories are either too large or too small to be of value in the analysis. It is emphasised, though, that the categorisation will be determined in advance of the regression models considering the relevant interactions, and that the primary subgroup analyses for this measure will be for the continuous version of the underlying variable.

7.7.3 Trial Centre Effect

Trial centre will be included in the regression models as a fixed effect to analyse the outcome measures. This will inform us of the effect that the trial centre has on each outcome.

8. ANALYSIS OF SAFETY

8.1. Adverse reactions

Data on adverse reactions and serious adverse reactions will also be collected and closely monitored to ensure the ongoing safety of participants. Adverse reactions will be recorded on a standardised adverse reactions report form. All serious adverse reactions will be notified to the trial sponsor (North Bristol NHS Trust) and reviewed by the Trial Steering Committee. Data on adverse reactions will be collected from trial questionnaires and during telephone contact with participants. Numbers of adverse reactions and their severity will be recorded in **Table 48**. Details of the adverse reactions will be presented in **Table 49** and **Table 50**.

Please refer to the trial protocol, section titled "Safety Reporting"

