3.6. Randomisation procedures

After patients have provided written, informed consent to participate and have completed and returned a baseline questionnaire, they will be randomly allocated to the STAR pathway or usual care. Randomisation will occur as soon as possible after the baseline questionnaire is received by the research team. Randomisation with allocation concealment will be conducted remotely via the Bristol Randomised Trials Collaboration using a web-based randomisation system. Randomisation will take place on a 2:1 basis to ensure that the intervention service is running at sufficient capacity to enable a pragmatic assessment of its effectiveness and, particularly, cost-effectiveness. If the intervention is operating to a sufficient degree of capacity per-protocol and CACE analyses will be more reliable and have higher power. To ensure reasonable balance between the two treatment groups, allocation will be minimised by pain in the replaced knee (assessed with both the Brief Pain Inventory Severity and the Brief Pain Inventory Interference Scales – these scores are both categorised using tertiles of STAR PACE data for these scores) and stratified by orthopaedic centre. Randomisation will be performed by a member of the research team at the co-ordinating centre and the local researcher at each site will then inform participants of the result.

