4. GENERAL ANALYSIS CONSIDERATIONS

4.1. Analysis populations

The primary analysis of the data will be on a complete case basis, in accordance as far as possible with the intention to treat (ITT) principle whereby we analyse as randomised, disregarding protocol deviations or non-compliance. Sensitivity analyses will utilise imputation methods to handle missing data to ascertain whether their exclusion in the primary analysis has had any effect within an ITT paradigm. In addition, a crude per protocol analysis will be performed using those patients who adhered with the intervention sufficiently. Adherence to the intervention, for a patient in the intervention arm, is defined as the patient attending their assessment clinic appointment and for patients in the control arm, adherence cannot be measured as they adhere by using usual care. We assume that all patients in the control arm have adhered to the intervention allocation. This per protocol analysis will address the same points as the comparison based on groups as allocated (hereafter referred to as 'the ITT analysis') just using a different population. Since these results are likely to be biased, we will also use the Complier Average Causal Effect (CACE) approach to adjust for any selection effects in terms of adherence.

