6.2. Data validation

The system will incorporate data entry and validation rules to reduce data entry errors, and management functions to facilitate auditing and data quality assurance. We will use a secure, web-based data collection platform (REDCap) which will be developed, validated, hosted and supported by the University of Bristol. Named blinded assessors perform data completeness checks of data and contact patients if there is missing data in their

questionnaires. This will reduce the amount of missing data as patients will have the opportunity to complete missing items over the phone. This may also be an opportunity to clarify any misunderstandings in the questionnaire. It is important for these telephone calls to be done by a member of a different trial centre team so that the researcher who phones the patient is unaware of the treatment group allocation. This is intended to minimise bias.

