6.4. Compliance

A complier to treatment is defined as a patient in the intervention arm who attends the assessment clinic or a patient in the control arm who complies with usual care (all patients in the control arm). Since non-compliance numbers are likely to be low, we set a rule to decide if we will use CACE analysis. If compliance is close to 100% then ITT analysis will be very similar to CACE analysis and so the latter will not be (additionally) informative.

If compliance is greater or equal to 95%, we will rule out the need for using CACE analysis. For compliance between 85% and 95% we will consider carrying out CACE analysis depending on the extent and pattern of adherence. For compliance below 85% we will use CACE analysis. Compliance rate will be recorded in **Figure 2**.

Compliance is recorded in **Table 46** by site and in total.

Descriptions of the number of follow up calls that the intervention group patients receive will be presented by site and in total. The time to first follow-up call will also be summarised by site and in total. These summaries can be found in **Table 47.**

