	randomised to	attend intervention	
	intervention group	appointment	
Site 1			

Site 2		
•••		
Total		

Table 47: Summaries of follow up calls received

	Site 1	Site 2	 Total
Number of patients in the			
intervention arm			
Number of patients to			
have received at least 1			
follow-up call			
Average number of			
follow-up calls received			
per intervention patient			
Average time to first			
follow-up call (in weeks)			

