8.9. Safety results

Table 48: Reporting Adverse reactions

Relatedness to trial in	Frequency	
Severity:	Not Serious	
	Serious unexpected	
	Serious expected	

Table 49: Adverse reactions

Adverse reaction	Site	Intervention/ Control

Table 50: Serious Adverse reactions

Adverse reaction	Site	Intervention/

Amendments to the SAP

Table 51: Amendments to the SAP

Previous version	Previous date	New version	New date	Brief summary of changes
V2.0	01.06.2017	V2.1	02.11.2017	Comments added following Oxford closure.
V2.1	02.11.2017	V2.2	11.06.2019	Added repeated measures analysis and added analysis to account for timings of clinics and subgroup analysis based on baseline PaSol.

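### The planned safety tables give no incidence of adverse reactions by arm under 2:1 allocation, and the SAP leaves open whether reactions are ascertained equally in the two arms

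*SAP*

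**What the plan says.** Section 8.1 names two sources of safety data: "Data on adverse reactions will be collected from trial questionnaires and during telephone contact with participants". It promises counts and severity in Table 48 and details in Tables 49 and 50, then refers to the protocol's Safety Reporting section. It specifies no rate, denominator or between-arm estimate.

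In section 8.9, "Table 48: Reporting Adverse reactions" has severity rows (not serious, serious unexpected, serious expected) and one frequency column. Table 49 is a line listing of reaction, site and arm, and Table 50 has the same layout for serious reactions.

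Section 3.6 sets the allocation: "Randomisation will take place on a 2:1 basis", intervention to control.

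Telephone contact appears in two other places:

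- Section 6.4, under Compliance: "Descriptions of the number of follow up calls that the intervention group patients receive will be presented by site and in total". The shell for this, "Table 47: Summaries of follow up calls received", has rows for intervention patients and none for controls.
- Section 6.2, on data validation: "Named blinded assessors perform data completeness checks of data and contact patients if there is missing data in their" questionnaires. These calls are open to both arms and are made by staff of another centre who do not know the allocation.

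Of the control arm, section 4.1 says that "adherence cannot be measured as they adhere by using usual care". The SAP describes no scheduled calls to controls.

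**The concern.** A reader of the final report will want to know what proportion of patients in each arm had an adverse reaction. Table 48 cannot show this because it pools the arms. Tables 49 and 50 carry the arm only as a label on each event, so the only between-arm information is the number of lines per arm. Under 2:1 allocation that number favours the smaller arm even when risk is equal. One patient with several reactions also cannot be told from several patients with one each, because the listings have no patient identifier and no table counts patients with an event.

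The second issue is ascertainment. If reactions are picked up during the intervention's follow-up calls and controls have no comparable contact, intervention patients have more occasions to report. Denominators would not remove that difference.

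At stake is whether the trial's safety output can be read by arm at all, and whether any difference seen reflects risk or frequency of contact.

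**Working it through.** **1. The plan's own figures.** Section 3.7 says that "a total of 380 participants randomised would yield 285 for analysis". Check: 380 × 0.75 = 285, which splits 2:1 into 190 and 95. With these arm sizes and a two-sided 5% test, power is 0.795 at 0.35 SD and 0.889 at 0.40 SD, matching the stated 80% to 90%. The design arithmetic is sound and confirms the 2:1 arm sizes.

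**2. Patients at risk by arm.** Intervention: 380 × 2/3 = 253.3. Control: 380 × 1/3 = 126.7. Rounded: 253 and 127.

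**3. Expected lines in the listings at equal risk and equal detection.** Expected count = arm size × risk. The SAP gives no risk, so three values are assumed, with one event per affected patient.

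| Assumed risk | Intervention | Control | Ratio |
|---|---|---|---|
| 2% | 253 × 0.02 = 5.1 | 127 × 0.02 = 2.5 | 1.99 |
| 5% | 253 × 0.05 = 12.7 | 127 × 0.05 = 6.4 | 1.99 |
| 10% | 253 × 0.10 = 25.3 | 127 × 0.10 = 12.7 | 1.99 |

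The ratio is 253/127 = 1.99 whatever the risk. Dividing each count by its own arm size gives a rate ratio of 1.00, so denominators remove this part completely.

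**4. Comparison with other shells in section 9.2.** Table 10 gives withdrawals by arm beside the number randomised, and Table 11 splits the count of protocol deviations by arm. Table 48 does neither. Section 1 allows table layout to change but says the content will follow the shells, so the missing arm split is planned content.

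**5. Ascertainment, as illustration only.** Suppose sources common to both arms capture a share q of reactions, extra intervention calls capture a share c of the remainder, and controls have no equivalent calls. With no true difference, the apparent rate ratio is [q + (1 − q)c]/q. Neither q nor c is in the SAP.

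| q | c = 0 | c = 0.25 | c = 0.50 | c = 0.75 |
|---|---|---|---|---|
| 0.9 | 1.00 | 1.03 | 1.06 | 1.08 |
| 0.7 | 1.00 | 1.11 | 1.21 | 1.32 |
| 0.5 | 1.00 | 1.25 | 1.50 | 1.75 |

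For example, q = 0.7 and c = 0.5 give (0.7 + 0.3 × 0.5)/0.7 = 0.85/0.7 = 1.21. The c = 0 column applies if follow-up calls add no detection, for instance because reactions are not recorded in them. The table shows the direction any effect would take under this model and how far its size depends on unknown inputs. It does not estimate what happened in this trial.

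**The case against.** The strongest objection is to the ascertainment argument. Section 8.1 does not limit telephone contact to one arm. No section says that reactions are elicited during the intervention's follow-up calls; section 6.4 and Table 47 count those calls as delivery of the intervention. The one telephone contact tied to data collection is the blinded missing-item call, open to both arms. How reactions are elicited is normally fixed in the protocol's safety section, which section 8.1 cites and which was not available for this check. This stands: the SAP supports the possibility of unequal detection, not its presence or size.

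Second, the plan has no formal between-arm safety test, so no test statistic is biased. The 2:1 imbalance misleads only someone who counts lines, and randomised numbers by arm appear in Table 10. This also stands, but a table that must be combined by hand with another and still yields no count of affected patients is not adequate safety reporting.

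Third, the plan records reactions, and what survives of the Table 48 header refers to relatedness. Equal risk in both arms may not be the natural expectation for events judged related to the intervention. This is fair, and the 1.99 ratio is therefore stated only as what equal risk would produce. Tables 49 and 50 do provide for control-arm reactions.

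Fourth, the shells are described as a guide and the text of Table 48 is partly cut off. The layout could change, but the readable part shows one frequency column and section 8.1 promises only numbers and severity.

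**Conclusion.** The reporting fault holds on the SAP's text. The planned safety tables give no incidence by arm, and at equal risk and equal detection the listings would show about twice as many intervention events (253/127 = 1.99). That figure rests only on the 2:1 ratio and the planned 380 patients.

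Unequal ascertainment is an open question. It follows as a possibility from sections 6.4 and 8.1 read together, but its size cannot be derived from the SAP. The illustrative ratios of 1.00 to 1.75 depend on assumed capture shares and on controls having no comparable contact.

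A reader might infer that the safety comparison is tilted against the intervention by design. The SAP does not support that. It does not say that reactions are collected in the follow-up calls or that controls lack equivalent contact, and it plans no formal comparison that could be tilted. A reader might also infer that a true difference could never be separated from these artefacts; for the allocation part this is wrong, because denominators remove it.

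**What to change.** 1. Split Table 48 by arm. For each arm give the number of patients with at least one reaction as n/N randomised (%), and the number of events by severity.
2. Show the source of detection (questionnaire, or telephone/clinic) in Tables 48 to 50 where the report form allows.
3. Report all-source incidence by arm as the main presentation. Give questionnaire-sourced incidence by arm as a supporting comparison, with a note that contact may differ between arms. Questionnaire-only events should not become the main comparison, because that would set aside reactions detected by telephone, some of which may be serious.
4. Check the protocol's Safety Reporting section for how reactions are elicited in each arm, and state the answer in section 8.1. If collection is the same in both arms, the note on unequal contact can be dropped.

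The cost is SAP wording and table columns. Source may have to be read from existing report forms, and the supporting comparison uses fewer events. Trial conduct and the efficacy analysis are unaffected.
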